2. BACKGROUND

2.1 Study Disease

Squamous cell carcinoma of the head and neck affects more than 61,760 people in the United States annually, with a 5-year survival rate being <60% (1,2). **The presence of lymph node (LN) metastasis is considered the most important negative prognostic factor for survival in patients with primary HNSCC (3,4).** Despite advanced anatomic and metabolic imaging techniques, occult LN (micro-) metastasis remain in the clinically and radiographically negative neck (cN0). In fact, 10 to 30% of cN0 patients present with occult LN metastasis (4). Even more so, treatment of the neck is often indicated when the risk of LN metastasis exceeds 15 to 20% (5,6). To address this surgically, the current NCCN guidelines recommend either elective regional neck node dissection or sentinel node (SN) biopsy (SNB) (7).

Elective lymph node dissection causes significant morbidity: The gold standard for detection of regional metastatic disease in HNSCC traditionally has been a (elective) neck dissection. However, shoulder dysfunction and pain due to accessory nerve (cranial nerve XI) injury are common after neck dissection (8–11). Moreover, 60 to 80% of subjects undergoing a neck dissection with sectioning of the nerve have pain, limited abduction of the shoulder, and anatomic deformities such as scapular flaring, droop, and protraction (12). To reduce morbidity, there has been a gradual migration away from extensive dissection to more limited dissection offered by SNB where only the primary tumor draining LN(s) are removed for detailed histologic examination (13–18). SNB has already replaced regional lymphadenectomy in melanoma and breast surgery to avoid the associated deficits associated with this more aggressive approach, and is now also advocated for HNSCC (7).

Sentinel node biopsy: SNB is performed as a surgical staging method to detect occult nodal disease in those tumor types with a high metastatic rate and where LN disease predicts outcome and informs adjuvant treatment decisions. Assuming the orderly spread of tumor cells through the lymphatic system (19), excision and evaluation of the primary tumor-draining LNs only (so-called SN(s)) will allow accurate determination of the tumor status of the regional LNs in the neck. SNB thus allows the selection of node-positive subjects that will benefit from additional surgical or adjuvant therapy, while sparing node-negative patients an unnecessary neck dissection.

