4. TREATMENT PLAN

4.1 Treatment Schedule

Subjects will receive intravenous panitumumab-IRDye800 (50 mg) 1 to 5 days prior to surgery. Then on the day before surgery, subjects in Cohort 1 will receive a local injection with 2 mCi Lymphoseek followed by lymphoscintigraphy and SPECT/CT imaging to determine the number and location of LNs. In the operation theatre, using a combination of fluorescence imaging and radio-tracing, the LNs of the neck will be evaluated and scored (Section 2.4, Figure 1).

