12. STATISTICAL CONSIDERATIONS

12.1 Statistical Design

12.1.1. Primary Objective and Endpoint

The **primary objective** of the study is to determine if near-infrared fluorescence imaging of panitumumab-IRDye800 can identify metastatic disease in regional neck LNs of subjects with HNSCC.

The **primary endpoint** is: The number and location of panitumumab-IRDye800 positive LNs that are also tumor-positive at (histo-)pathology.

To **answer the primary objective**, we will calculate the sensitivity and specificity of the intraoperative findings on whether the LN is fluorescent (ie, presence of panitumumab-IRDye800) to the histopathological (gold standard) status of the LNs.

We will use the matched pair Durkalski's test (80), accounting for the cluster-correlation within subject, for all sensitivity and specificity comparisons (primary and secondary) using the clust.bin.pair package (81) in the R statistical software (84). Significance for both primary and secondary analyses will be assessed at the 0.05 level and to assess uncertainty, 95% confidence intervals will be provided for all estimates.

Descriptive statistics for continuous characteristics (eg, size of the tumor compartment) will include mean, standard deviation, median, interquartile range, minimum, and maximum values. Frequencies and percentages will be used to summarize categorical data. Graphical tools such as heat maps, histograms, and boxplots will be used to assess distributional properties of continuous variables.

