12.1.3. Sample Size Justification and Power Considerations

We expect to enroll 10 T1/T2 node-negative subjects and 10 subjects with T1-4 and LN metastasis. Based on the data on LN collection from our current IRB-35064 study, we expect that 50% of subjects will undergo a bilateral neck dissection, meaning we would have a total of 30 necks. Assuming an average of 20 LN harvested per neck we would have a total of 600 LNs. Based on previous findings from our IRB-35064 study, we expect approximately 30-40% of subjects (6 to 8 of 20) will have metastatic LNs with an overall prevalence of 5 to 10% of the total number of harvested LNs (30 to 60 of 600) being tumor-positive.

Since this is a Phase 2 study, power considerations are limited but even so, we have excellent power to detect differences in specificity. Although we will use Durkalski's test to compare sensitivities and specificities, we estimated power by first determining the effective sample size (ESS), adjusting for the correlation of LNs within person, and then estimated power using McNemar's test on this ESS. We assumed an intra-class correlation of 0.005, yielding an effective sample size of 524 LNs. With an effective sample size of 524, a prevalence of 7.5%, a significance level of 0.05, and a 0.25 proportion of discordant pairs, we have greater than 99% power to detect a 0.1 difference in specificities, assuming the lower specificity is 0.8. Similarly, we have greater than 78% power to detect a 0.2 difference in sensitivity with the one-sided McNemar test. This assumes the proportion of discordant pairs is 0.25 and the lower sensitivity is 0.75.

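### With the 1 to 3 node-positive subjects expected in Cohort 1, the planned Durkalski test of sensitivity has almost no ability to reject, so non-significance says little about equal accuracy of the two tracers

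*Combined protocol and SAP*

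**What the plan says.** Section 12.1.1 applies Durkalski's test, "accounting for the cluster-correlation within subject, for all sensitivity and specificity comparisons (primary and secondary"), and adds: "Significance for both primary and secondary analyses will be assessed at the 0.05 level". It gives no sidedness and no minimum number of node-positive subjects.

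On who contributes data, Section 12.1.3 states: "We expect to enroll 10 T1/T2 node-negative subjects and 10 subjects with T1-4 and LN metastasis". Under Section 4.1, "subjects in Cohort 1 will receive a local injection with 2 mCi Lymphoseek"; Table 1 lists none for Cohort 2. Section 2.1 reports that "10 to 30% of cN0 patients present with occult LN metastasis". For all 20 subjects together, Section 12.1.3 says "we expect approximately 30-40% of subjects (6 to 8 of 20) will have metastatic LNs".

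On power, Section 12.1.3 acknowledges that Durkalski's test will be used but calculates with McNemar's test on an effective sample of 524 nodes pooled over both cohorts, concluding: "we have greater than 78% power to detect a 0.2 difference in sensitivity with the one-sided McNemar test".

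The secondary objective is stated as equal accuracy of the two tracers (Section 1.2). The synopsis compares Lymphoseek's sensitivity and specificity with fluorescence. Section 12.1.2 compares them, by Durkalski's test, with neck dissection.

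**The concern.** Durkalski's test treats the subject as the independent unit. Only subjects with at least one tumor-positive node enter a sensitivity comparison, and only Cohort 1 has both tracers. The test may therefore rest on one, two or three independent units, however many nodes are examined. The power paragraph counts nodes, so it does not show this.

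What is at stake is interpretation. The objective is equality, no equivalence margin is set, and the protocol says that false negatives are the particular worry. A p-value that stays above 0.05 under almost any data could be taken as support for equal accuracy.

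**Working it through.** **1. The plan's own figures.** Nodes per subject: 600/20 = 30. Effective sample size: 600/(1 + 29 × 0.005) = 524.0, as stated. Positive nodes: 524 × 0.075 = 39.3. A discordant proportion of 0.25 and a difference of 0.2 give cell probabilities 0.225 and 0.025. Exact one-sided McNemar power is 78.2% with 40 nodes and 76.8% with 39 (normal approximation 82.7%). The stated figure reproduces. The exact two-sided equivalent is 66 to 68%.

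**2. The ceiling.** For subject k with n_k tumor-positive nodes, let x_k = (b_k − c_k)/n_k, where b_k and c_k count nodes found by one method only. The standard statistic is X² = (Σx_k)²/Σx_k². By Cauchy-Schwarz, X² ≤ K, the number of subjects with x_k ≠ 0. Random tables (100,000 for each K from 1 to 5) reached K and never exceeded it. The cut-off is 3.841 two-sided and 1.645² = 2.706 one-sided.

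| K | Largest X² | Smallest two-sided p | Smallest one-sided p |
|---|---|---|---|
| 1 | 1 | 0.317 | 0.159 |
| 2 | 2 | 0.157 | 0.079 |
| 3 | 3 | 0.083 | 0.042 |
| 4 | 4 | 0.0455 | 0.023 |

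When all x_k share a sign, X² = K/(1 + CV²), where CV is their coefficient of variation. At K = 4, two-sided rejection needs CV ≤ √(4/3.841 − 1) = 0.20: all four subjects in one direction and nearly equal in size.

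**3. How many subjects Cohort 1 supplies.** 10 × 10% to 10 × 30% gives 1 to 3 expected. K cannot exceed the number of node-positive subjects, so the binomial chance of 4 or more in 10 caps the chance of any two-sided rejection:

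| Rate | P(4 or more of 10) |
|---|---|
| 10% | 1.3% |
| 20% | 12.1% |
| 30% | 35.0% |
| 34% (upstaging rate cited in Section 2.1) | 45.9% |

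**4. Power when four or more occur.** Simulation used the plan's 0.225 and 0.025, with an assumed 1 to 5 positive nodes per subject, independent. Two-sided power is zero at 3 subjects, 0.2 to 2.6% at 4, and 2.4 to 33% at 6.

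A generous bound at a 30% rate with 5 nodes each gives 5 subjects the power found for 6, and 8 or more subjects a power of 1: 0.2001 × 0.026 + (0.1029 + 0.0368) × 0.334 + 0.0090 × 0.486 + 0.0016 = 0.058. Overall two-sided power is thus below 6%.

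**5. Durkalski power on the pooled inputs.** This uses 39 positive nodes, the same discordance and an ICC of 0.005. It supposes that both methods are read in every positive subject, which the design does not provide for the two tracers.

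| Split of nodes across 6 to 8 positive subjects | Two-sided | One-sided |
|---|---|---|
| Even | about 43–59% | about 75–80% |
| Uneven (assumed Dirichlet) | about 25–42% | about 64–72% |

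If all 10 Cohort 2 subjects are node-positive, adding 1 to 3 from Cohort 1 gives 11 to 13. At 12 with an even split, power is about 69% two-sided and 84% one-sided.

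**The case against.** **Rejection is not impossible.** A reader might infer that non-significance is guaranteed. The documents do not support that. The only sidedness they state for sensitivity is one-sided, in the power paragraph. One-sided, three subjects can just reach 0.042. Simulated one-sided power is 1 to 13% at 3 subjects and 4 to 35% at 4, under the assumptions of step 4. The figure of 1 to 3 is derived from a background sentence and is an expectation; applying the 30 to 40% of Section 12.1.3 to ten subjects gives 3 to 4. This stands. The supportable statement is near-zero power two-sided and low power one-sided.

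**The stated power is not refuted like for like.** It is tempting to set 43–59% against 78%, but that compares a two-sided test with a one-sided one. One-sided with an even split, Durkalski's test gives 75–80%, essentially the stated figure. The real gaps are the missing sidedness, the sensitivity to uneven splitting, and pooling over subjects who receive no Lymphoseek.

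**The plan may not run this test.** Section 12.1.2 names neck dissection as the comparator and gives only relative false-negative odds for the two tracers. However, the synopsis compares with fluorescence, and Section 12.1.1 covers every sensitivity comparison. Section 3.1 makes the cohorts sentinel-node-only or neck-dissection-only, so no subject is planned to have both Lymphoseek and neck dissection.

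**Nobody says that p > 0.05 proves equality.** True: no section does so, and Section 12.1.1 requires 95% intervals for all estimates. The misreading is a risk and is not a stated rule. Also, Cohort 1 harvest follows the gamma probe (Section 2.4.3.3), so Lymphoseek could hardly be shown to miss a node. That is a separate limit which no choice of test removes.

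**Conclusion.** The concern holds for the Cohort 1 sensitivity comparison of fluorescence with Lymphoseek. With three or fewer node-positive subjects the two-sided test cannot reach 0.05. A fourth subject permits rejection only in near-unanimous data, with power under 3% on the plan's discordance rates. A non-significant result would carry almost no information about equal accuracy.

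This rests on the standard form of the statistic, the 10 to 30% occult rate (the 34% rate does not change the conclusion for a two-sided test), and an assumed 1 to 5 positive nodes per subject for the power figures. The ceiling itself needs no such assumption.

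Specificity is not affected by this argument: up to 10 subjects can contribute in Cohort 1, well above the cut-off. The power figure is correct arithmetic for a one-sided McNemar test on about 39 to 40 pooled nodes; it does not describe the Cohort 1 comparison. Two inconsistencies add to the problem: the secondary comparator, and an expected 6 to 8 positive subjects of 20 beside ten Cohort 2 subjects described as having nodal metastasis.

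Severity is should-fix, since this is a secondary comparison in a study that calls itself exploratory.

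**What to change.** - For Cohort 1 sensitivity, replace the significance test with paired results listed subject by subject, and the sensitivity difference with a subject-level interval. With very few positive subjects, label it descriptive.
- State that non-significance is not evidence of equal accuracy.
- State the sidedness of any Durkalski test that is kept. Replace the 78% with its simulated power at that sidedness, over a stated range of positive subjects and of node splits.
- Reconcile the secondary comparator between the synopsis and Section 12.1.2, and the two statements in Section 12.1.3 on how many subjects will be node-positive.

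Cost: SAP wording and one simulation. No new data are needed. The stated power will probably become less favorable.

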12.1.2. Secondary Objective and Endpoint

The **secondary objective** of the study is to determine if panitumumab-IRDye800 can identify LNs with the same efficiency as Lymphoseek.

The **secondary endpoint** is: The number and location of Lymphoseek positive LNs that are also tumor-positive at (histo-)pathology.

To answer the secondary objective: We will determine if the LN tracer Lymphoseek can identify metastatic disease in regional neck LNs of subjects with HNSCC. Similar to the primary analysis, we will calculate the specificity and sensitivity of Lymphoseek for metastatic LN identification, using histology as the gold standard, and compare these to neck dissection with Durkalski's test. Since false negatives are of particular concern, we will calculate the odds of obtaining a false negative using panitumumab-IRDye800 relative to the odds of obtaining a false negative using Lymphoseek-based SNB.

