STATISTICAL CONSIDERATIONS	
To answer the primary objective we will calculate the sensitivity and specificity of the intraoperative findings on whether the lymph node is fluorescent (ie, presence of panitumumab-IRDye800) to the histopathological (gold standard) status of the lymph nodes.
 
Analysis for the secondary objective: We will determine if panitumumab-IRDye800 can identify sentinel nodes with the same accuracy as Lymphoseek. Similar to the primary analysis, we will calculate the specificity and sensitivity of Lymphoseek for metastatic lymph node identification, using histology as the gold standard, and compare these to the fluorescence imaging-based results. Since false negatives are of particular concern, we will calculate the diagnostic odds ratio to better understand the odds of obtaining a false negative using panitumumab-IRDye800 relative to the odds of obtaining a false negative using Lymphoseek-based sentinel node biopsy.

STUDY SCHEME

[figure not shown]

Figure 1. Schematic overview of the clinical trial in which we will directly compare panitumumab-IRDye800 to the reference standards sentinel node biopsy and neck dissection. Key steps of the clinical study are mentioned.

LIST OF ABBREVIATIONS AND DEFINITION OF TERMS

^{99m} Tc	Technetium-99m
AE	Adverse Event
BID	Twice Daily
BSA	Body Surface Area
CBC	Complete Blood Count
CI	Confidence Interval
CMAX	Maximum Concentration of Drug
CNS	Central Nervous System
CRF	Case Report/Record Form
CT	Computed Tomography
CTCAE	Common Terminology Criteria for Adverse Events
DLT	Dose-Limiting Toxicity
DSMC	Data Safety Monitoring Committee
ECG	Electrocardiogram
ECOG	The Eastern Cooperative Oncology Group
EGFR	Epidermal Growth Factor Receptor
eLND	Extensive Lymph Node Dissection
FDA	Food and Drug Administration
GMP	Good Manufacturing Practice
Hgb	Hemoglobin
HNSCC	Head and Neck Squamous Cell Carcinoma
HTN	Hypertension
ICG	Indocyanine green
ILD	Interstitial Lung Disease
IND	Investigational New Drug
IRB	Institutional Review Board
IV	Intravenous
LLN	Lower Limit of Normal
LN	Lymph Node
MTD	Maximum Tolerated Dose
NIR	Near-Infrared
NHS	N-hydroxysuccinimide
PAI	Photoacoustic imaging
PLT	Platelet
ROI	Region of Interest
SAE	Serious Adverse Event
SN	Sentinel Node
SNB	Sentinel Node Biopsy
SNR	Signal to Noise Ratio
SPECT	Single Photon Emission Computed Tomography
TBR	Tumor to Background Ratio
ULN	Upper Limit of Normal
UNK	Unknown
WBC	White Blood Cell
WHO	World Health Organization

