1.2. Secondary Objective

Determine if panitumumab-IRDye800 can identify sentinel nodes with the same accuracy as Lymphoseek.

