Sentinel node biopsy vs elective regional node dissection: Besides decreased morbidity, SNB offers other advantages over a neck dissection: i) Identification of aberrant draining patterns and “skip metastasis” (35–37); and ii) Improved (micro-) metastasis identification at (histo-)pathology; fewer SNs are harvested which are more meticulously evaluated by the pathologist, resulting in improved diagnostic accuracy (38,39). However, challenges remain: i) Local tracer injection is complicated in areas deep in the oral cavity; ii) Near-injection site SN identification can be challenging due to overshadowing of signal at the primary tumor signal (40,36,22); iii) Often multiple SNs are identified during surgery (22) increasing the risk of complications (41) (eg, nerve damage, lymphedema, scar tissue formation); iv) neck dissection after a positive SNB is complicated due to the presence of scar tissue; and v) A false-negative SNB occurs in 3 to 10% of subjects (ie, the SN is tumor-negative, but at follow-up metastasis in remaining regional LNs are found (42–45). Moreover, although LN mapping is superior to radiographic and clinical exam, it is still limited by the need for direct injection of the dye or radiolabeled compound. **Upstaging with LN assessment can thus only be assessed in tumor types that are accessible for local injection.** This is significant because it influences standard of care (LN surgery or complete lymphadenectomy) in these subject populations only. Identification of regional disease will inform prognostic information and/or determine the need and extent of adjuvant therapies for additional tumor types. Most importantly, however, the tracers used for SNB are not tumor-specific and thus SNB, similar to neck dissection, does not allow for intraoperative tumor-positive LN identification (21,46,47). In fact, **for both SNB and neck dissection (histo-)pathological evaluation is required to determine the presence of (micro-) metastasis and thus a method to intraoperatively identify metastatic LNs is lacking.** Thus, HNSCC subjects would benefit from an alternative technique that, allows for intraoperative lymph node staging.

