2.4.2. Dosing

Subjects will be infused with 50 mg panitumumab-IRDye800 and 2 mCi Lymphoseek. Panitumumab-IRDye800 will be systemically infused 1 to 5 days prior to surgery, whereas 2 mCi Lymphoseek will be administered locally on the day before surgery (Table 1).

Table 1: Cohort structure

Cohort	Preoperative nodal stage	Number of subjects	Dose panitumumab-IRDye800	Dose Lymphoseek
1	T1 or T2 stage and node negative (ie, cN0)	10	50 mg	2 mCi
2	Any T stage and node positive (ie, cN+)	10	50 mg	none

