2.4.3.3. Intraoperative Imaging Protocol

On the day of surgery, 1 to 5 days post-infusion of panitumumab-IRDye800, intraoperative fluorescence imaging and gamma tracing will be performed.

Optical imaging devices to be used: Imaging with the optical imaging devices will be performed intraoperatively *in situ* and on the back table (see Appendix B for a list of the imaging devices). Additional ex vivo devices will also be used to image the specimens on the back table (see Appendix B for a list of the imaging devices).

All in vivo devices are FDA approved for measuring intraoperative blood flow after indocyanine green (ICG) injection. Because IRDye800 and ICG have overlapping excitation and emission spectra, each device can also be used for imaging subclinical disease based on our preclinical studies in head and neck cancer (see Appendix B for a list of the imaging devices).

Sentinel node biopsy (stage T1/2, cN0)

Step 1) *In situ* gamma tracing and fluorescence imaging of the sentinel nodes:

1. Prior to opening the skin, the surgeon will screen the neck for the presence of radioactive node(s) (ie, SNs) by sweeping the gamma probe over the intact neck. If any radioactive nodes are detected, the location of detected radioactive nodes will be marked on the skin using indelible ink and a still image of the marked will be collected for documentation.
2. After opening the skin, a photo of the neck will be taken for documentation. Hereafter the surgeon will perform fluorescence imaging of the neck to evaluate if there are any fluorescent nodes visible. Fluorescent nodes will be marked on the photo of the neck. Video and still images of the fluorescence imaging procedure will be collected.

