3. Hereafter, as per standard of care, the surgeon will perform SNB using the gamma probe. For this, the surgeon will evaluate the neck with the gamma probe for the presence of radioactive nodes. Upon localizing of radioactive nodes, the count rate of the node will be determined. Then, just prior to the resection of the radioactive node, *in situ* fluorescence imaging will be performed to evaluate the fluorescence-based visibility of the node. For each radioactive node, the respective *in situ* location will be documented (level Ia, Ib, IIa, IIb, III, IV or V) as well as the radioactive status (count rate) and fluorescence status (yes/no). Hereafter the node will be harvested by the surgeon. This process will be repeated until no radioactive nodes are detected anymore *in situ*.

Step 2) Wound bed imaging:

As per standard of care SNB, upon completion of SNB, the neck will be screened once more with the gamma probe as such to determine the presence of any remaining radioactivity (ie, a radioactive signal detected > 10% of the background that correlates with any substrate (node). Areas in the wound bed determined radioactive-positive will be surgically re-evaluated, and, upon checking the fluorescence-status, removed, if deemed necessary by the surgeon. If any nodes are found, gamma tracing will be performed to determine the radioactive status.

Step 3) Pathological imaging:

The fluorescence and/or radioactive status of all excised nodes will be confirmed *ex vivo* on the back table using both a closed-field imaging device and an open-field device as well as the gamma probe, respectively. Hereafter all excised nodal specimens will be sent for (histo-)pathology. After the tissue has been processed and evaluated by the pathologist, imaging findings will be compared to gold-standard histological-assessment performed by the pathologist (including a hematoxylin and eosin (H&E) staining) to determine the correlation between fluorescence, radioactivity and the presence/absence of tumor tissue in the LN(s). Also findings will be compared to preoperative lymphoscintigraphy and SPECT/CT imaging (ie, correlation between preoperative imaging findings and intraoperative imaging findings).

Neck dissection only (T1-4, cN+)

After the neck has been opened by the surgeon, it will be inspected by the surgeon for the presence of suspicious nodes. Real-time fluorescence imaging of the LNs in the neck will then be performed at 4 time points:

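### Section 12.1.2 tests Lymphoseek against neck dissection, which makes no per-node call of its own; no margin supports the equal-accuracy aim, and the 78% power does not apply to Cohort 1 alone

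*Combined protocol and SAP*

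**What the plan says.** The secondary objective is worded in two ways. Section 1.2 has "Determine if panitumumab-IRDye800 can identify sentinel nodes with the same accuracy as Lymphoseek"; Section 12.1.2 has "determine if panitumumab-IRDye800 can identify LNs with the same efficiency as Lymphoseek". Both set one tracer against the other.

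The analysis text does not agree on the comparator:

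- Section 12.1.2 obtains Lymphoseek's sensitivity and specificity "using histology as the gold standard, and compare these to neck dissection with Durkalski's test". Its only tracer-against-tracer quantity is a relative odds of a false negative, with no test attached.
- The synopsis (Statistical Considerations) obtains the same quantities "using histology as the gold standard, and compare these to the fluorescence imaging-based results".
- Section 10.2 includes the Lymphoseek-versus-fluorescence comparison in the secondary endpoint.
- Section 12.1.1 assigns Durkalski's test, the 0.05 level and 95% confidence intervals to primary and secondary comparisons alike.

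On what neck dissection can deliver, Section 2.1 says that "for both SNB and neck dissection (histo-)pathological evaluation is required to determine the presence of (micro-) metastasis". Table 1 in Section 2.4.2 gives Lymphoseek to Cohort 1 (10 subjects) and none to Cohort 2 (10 subjects). Section 12.1.3 states more than 78% power for a 0.2 difference in sensitivity with a one-sided McNemar test, based on 600 nodes from all 20 subjects.

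**The concern.** A matched-pair test needs two separate readings on each node, both judged against a reference. In Section 12.1.2 the second reading comes from neck dissection, which does not classify nodes. An analyst following that section would have no usable second arm and would not be answering the secondary objective.

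The likely recourse is the synopsis comparison. That raises a second problem: the aim is sameness, while the tool is a difference test with no margin. In a small cohort a non-significant result is the expected outcome even when the tracers differ materially, and it could be reported as equal accuracy. The 78% figure could then be cited as reassurance, although it was calculated on twice as many subjects as receive both tracers.

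**Working it through.** **1. Is neck dissection a usable comparator?** There are two ways to give it a per-node reading. If the reading is the pathology result, it equals the gold standard and scores 100% sensitivity and 100% specificity by construction. If the reading is that the node was removed, every examined node is positive, giving 100% sensitivity and 0% specificity. Neither is informative, and this holds whether or not Cohort 1 is dissected. If Cohort 1 has sentinel node biopsy only (Section 3.1 permits one surgical criterion per subject, and Section 2.4.3.3 describes harvest of radioactive nodes), there are also no nodes with both a Lymphoseek reading and a dissection.

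**2. Reproduce the plan's power.** Inputs from Section 12.1.3: 600 nodes, 20 subjects (30 nodes each), intra-class correlation 0.005, prevalence 7.5%, discordance 0.25, difference 0.2, alpha 0.05.

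- Design effect = 1 + (30 − 1) × 0.005 = 1.145; 600 / 1.145 = 524, as stated.
- Positive nodes = 524 × 0.075 = 39.3, rounded up to 40.
- Discordant probabilities: p10 + p01 = 0.25 and p10 − p01 = 0.20, so p10 = 0.225 and p01 = 0.025. A discordant pair favours the better tracer with probability 0.225 / 0.25 = 0.9.
- Exact power = Σ over m of P[Bin(N, 0.25) = m] × P[Bin(m, 0.9) ≥ c(m)], where c(m) is the smallest count with P[Bin(m, 0.5) ≥ c] ≤ 0.05 (0.025 if two-sided).
- At N = 40, one-sided: 78.1%. The stated figure reproduces.

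**3. Apply it to Cohort 1.** Assumptions: Cohort 1 is dissected, supplies half the nodes (300 / 1.145 = 262 effective), and has 5% to 7.5% positive. Then 262 × 0.05 = 13.1 and 262 × 0.075 = 19.7, or about 13 to 20 positive nodes.

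| Effective positive nodes | Exact one-sided | Exact two-sided |
|---|---|---|
| 40 (plan, all subjects) | 78% | 68% |
| 20 | 34% | 20% |
| 13 | 12% | 4% |
| 6 | 0.3% | 0.01% |

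At 20 nodes the exact two-sided test is non-significant about 80% of the time when the sensitivities truly differ by 0.2, and 96% of the time when they differ by 0.1.

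**4. Why 13 to 20 is optimistic.** Step 3 applies the whole-study prevalence to clinically node-negative necks. Section 2.1 puts occult metastasis at 10% to 30% of such patients, or 1 to 3 of 10. Section 12.1.3 expects 30 to 60 positive nodes in 6 to 8 subjects. Pairing low with low and high with high gives 30 / 6 = 5 to 60 / 8 = 7.5 per node-positive subject. So 1 × 5 = 5 to 3 × 7.5 = 22.5 raw nodes, and dividing by 1.145 gives about 4 to 20 effective positive nodes from 1 to 3 people. Twenty is the ceiling of that range. At 4 nodes the exact one-sided test cannot reach significance, since 0.5^4 = 0.0625.

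**5. Precision.** The approximate 95% half-width for the paired difference when the true difference is zero is 1.96 × √(0.25 / N): 0.22 at 20 nodes and 0.40 at 6.

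**The case against.** The strongest reply is that the tracer comparison is already specified: the synopsis and Section 10.2 name it, and Section 12.1.1 supplies the test and the intervals. On that view only one phrase in Section 12.1.2 is out of line. This largely stands. A reader might infer that the plan has no tracer comparison at all, and the documents do not support that. The defect is a comparator that conflicts with the other sections and cannot serve as a paired arm.

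A reader might also infer that the named test has zero pairs whatever happens. That holds only if Cohort 1 is not dissected. Sections 2.4.3.3 and 3.1 point to biopsy only. Section 4.5 refers to lymphadenectomy alongside Cohort 1 gamma tracing, and Section 12.1.3 counts dissected necks across all subjects. The study scheme figure is not available to settle it. The degeneracy in step 1 does not depend on the answer.

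Third, Section 2.4.1 calls the study exploratory, Section 12.1.3 concedes that power is limited, and no passage says that non-significance will be read as sameness. That is fair, so the misreading is a risk rather than a stated intention. The objective is nevertheless worded as sameness, and nothing in the plan says how it would be judged.

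Finally, it is tempting to say that Lymphoseek's sensitivity is bound to come out near 100%. Under biopsy only, harvest is driven by radioactivity ("This process will be repeated until no radioactive nodes are detected anymore"), whereas before harvest "Fluorescent nodes will be marked on the photo of the neck". Lymphoseek-negative nodes would then largely lack histology. This too is conditional on the unresolved Cohort 1 surgery and does not carry the point.

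**Conclusion.** The concern holds in three parts. The comparator in Section 12.1.2 cannot function in a matched-pair test and contradicts the synopsis and Section 10.2. No margin is given, so a non-significant difference cannot support equal accuracy or equal efficiency. The 78% power is correctly calculated for 40 effective positive nodes, but it does not describe the tracer comparison.

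For Cohort 1 the exact power for a 0.2 sensitivity difference is about 12% to 34% one-sided and 4% to 20% two-sided. This assumes dissection, half of the effective nodes, 5% to 7.5% prevalence, and the plan's own discordance and correlation. At 6 effective positive nodes, well within the 4 to 20 implied by the plan's figures for node-negative patients, one-sided power is below 1%. With positive nodes coming from perhaps 1 to 3 people, any node-level power is only indicative.

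This should be corrected before analysis. The calculation of fluorescence sensitivity and specificity for the primary objective is not affected.

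**What to change.** - **Section 12.1.2:** replace neck dissection as the comparator with panitumumab-IRDye800 fluorescence on histologically verified Cohort 1 nodes, in line with the synopsis and Section 10.2. Report paired differences in sensitivity and specificity with cluster-adjusted 95% intervals, and show false-negative counts beside the odds ratio.
- **Interpretation:** label the comparison descriptive and state that no claim of equal accuracy or efficiency will be drawn from a non-significant test.
- **Section 12.1.3:** state that the 78% does not apply to the tracer comparison. Give the Cohort 1 figure with its assumed number of positive nodes, the sidedness and the McNemar version used.
- **Cohort 1 surgery:** Sections 2.4.3.3, 3.1, 4.5 and 12.1.3 must be reconciled on whether Cohort 1 is dissected. If nodes are harvested only because they are radioactive, describe the result as fluorescence detection among Lymphoseek-positive nodes.

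The cost is a rewording of Section 12.1.2 and one power statement in Section 12.1.3, with no new data. The reconciliation is a protocol clarification rather than SAP wording alone. The downside is that the secondary conclusion will probably be descriptive.
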